9.3 Schedule of Observations and Procedures

The schedule for all study-related procedures for all evaluations is shown in [Appendix A](#).

Assessments should be completed at the designated visit/time point(s).

9.4 Biological Sample Retention and Destruction

In this study, specimens for genome/gene analysis will be collected as described in Section 9.1.15. The genetic material will be preserved and initially stored at **PPD** Central Laboratory and then at **PPD** for up to but not longer than 15 years or as required by applicable law. The sponsor has put into place a system to protect the subjects' personal information to ensure optimal confidentiality and defined standard processes for sample and data collection, storage, analysis, and destruction.

The sponsor and researchers working with the sponsor will have access to the samples collected and any test results. All samples collected during the study will be stored securely with limited access and the sponsor will require anyone who works with the samples to agree to hold the research information and any results in confidence.

The sample will be labeled with a unique sample identifier similar to labeling in the main study but using a code that is different from the code attached to the health information and other clinical test results collected in the study. The sample and data are linked to personal health information with code numbers. This link means that the subject may be identified but only indirectly. The code numbers will be kept secure by or on behalf of the sponsor.

Subjects who consented and provided PGx blood samples for DNA and RNA analysis can withdraw their consent and request disposal of a stored sample at any time. The sponsor should be notified of any withdrawal of consent. Notify sponsor of consent withdrawal.

10.0 PRETREATMENT EVENTS AND ADVERSE EVENTS

10.1 Definitions

10.1.1 PTEs

A PTE is defined as any untoward medical occurrence in a clinical investigation subject who has signed informed consent to participate in a study but prior to administration of any study drug; it does not necessarily have to have a causal relationship with study participation.

10.1.2 AEs

An AE is defined as any untoward medical occurrence in a clinical investigation subject administered a drug; it does not necessarily have to have a causal relationship with this treatment.

An AE can therefore be any unfavorable and unintended sign (eg, a clinically significant abnormal laboratory value), symptom, or disease temporally associated with the use of a drug whether or not it is considered related to the drug.

10.1.3 Additional Points to Consider for PTEs and AEs

An untoward finding generally may:

- Indicate a new diagnosis or unexpected worsening of a pre-existing condition. (Intermittent events for pre-existing conditions or underlying disease should not be considered PTEs or AEs.)
- Necessitate therapeutic intervention.
- Require an invasive diagnostic procedure.
- Require discontinuation or a change in dose of study drug or a concomitant medication.
- Be considered unfavorable by the investigator for any reason.

PTEs/AEs caused by a study procedure (eg, a bruise after blood draw) should be recorded as a PTE/AE.

Diagnoses vs signs and symptoms:

- Each event should be recorded to represent a single diagnosis. Accompanying signs (including abnormal laboratory values) or symptoms should NOT be recorded as additional AEs. If a diagnosis is unknown, sign(s) or symptom(s) should be recorded appropriately as a PTE(s) or as an AE(s).

Laboratory values findings:

- Changes in laboratory values are only considered to be PTEs or AEs if they are judged to be clinically significant (ie, if some action or intervention is required or if the investigator judges the change to be beyond the range of normal physiologic fluctuation). A laboratory re-test and/or continued monitoring of an abnormal value are not considered an intervention. In

addition, repeated or additional noninvasive testing for verification, evaluation, or monitoring of an abnormality is not considered an intervention.

- If abnormal laboratory values are the result of pathology for which there is an overall diagnosis (eg, increased creatinine in renal failure), the diagnosis only should be reported appropriately as a PTE or as an AE.

Pre-existing conditions:

- Pre-existing conditions (present at the time of signing of informed consent) are considered concurrent medical conditions and should NOT be recorded as PTEs or AEs. Baseline evaluations (eg, laboratory tests, X-rays) should NOT be recorded as PTEs unless related to study procedures. However, if the subject experiences a worsening or complication of such a concurrent medical condition, the worsening or complication should be recorded appropriately as a PTE (worsening or complication occurs before start of study drug) or an AE (worsening or complication occurs after start of study drug). Investigators should ensure that the event term recorded captures the change in the condition (eg, “worsening of...”).
- If a subject has a pre-existing episodic concurrent medical condition (eg, asthma, epilepsy) any occurrence of an episode should only be captured as a PTE/AE if the condition becomes more frequent, serious or severe in nature. Investigators should ensure that the AE term recorded captures the change in the condition from Baseline (eg “worsening of...”).
- If a subject has a degenerative concurrent medical condition (eg, cataracts, rheumatoid arthritis), worsening of the condition should only be recorded as a PTE/AE if occurring to a greater extent to that which would be expected. Investigators should ensure that the AE term recorded captures the change in the condition (eg, “worsening of...”).

Worsening of PTEs or AEs:

- If the subject experiences a worsening or complication of a PTE after the start of study drug, the worsening or complication should be recorded appropriately as an AE. Investigators should ensure that the AE term recorded captures the change in the PTE (eg, “worsening of...”).
- If the subject experiences a worsening or complication of an AE after any change in study drug, the worsening or complication should be recorded as a new AE. Investigators should ensure that the AE term recorded captures the change in the condition (eg, “worsening of...”).

Changes in intensity of AEs /Serious PTEs:

- If the subject experiences changes in intensity of an AE/serious PTE, the event should be captured once with the maximum intensity recorded.

Preplanned procedures (surgeries or interventions):

- Preplanned procedures (surgeries or therapies) that were scheduled prior to signing of informed consent are not considered PTEs or AEs. However, if a preplanned procedure is performed early (eg, as an emergency) due to a worsening of the pre-existing condition, the

worsening of the condition should be recorded as a PTE or an AE. Complications resulting from any planned surgery should be reported as AEs.

Elective surgeries or procedures:

- Elective procedures performed where there is no change in the subject's medical condition should not be recorded as PTEs or AEs, but should be documented in the subject's source documents. Complications resulting from an elective surgery should be reported as AEs.

Insufficient clinical response (lack of efficacy):

- Insufficient clinical response, efficacy, or pharmacologic action, should NOT be recorded as an AE. The investigator must make the distinction between exacerbation of pre-existing illness and lack of therapeutic efficacy.

Overdose:

- Cases of overdose with any medication without manifested side effects are NOT considered PTEs or AEs, but instead will be documented on an Overdose page of the eCRF. Any manifested side effects will be considered PTEs or AEs and will be recorded on the AE page of the eCRF.

Suicidality events:

- A completed suicide is always an SAE based on its fatal outcome. Additionally, for the purpose of this development program, active suicidal behaviors such as "suicidal intention with a definite plan" and "suicide attempt" will also be collected as SAEs. Unless the event meets other serious criteria, suicidal thoughts or suicidal ideations that do not include a definite plan or action will be collected as nonserious AEs in accordance with the standard AE reporting requirements (eg, if a pre-existing suicidal ideation recorded on the screening C-SSRS got worse during the study, it should be reported as an AE). A subject presenting with self-mutilation or other types of self-injury should be questioned by the investigator to clarify if the action was suicidal in intent. If the event was suicidal in intent, the investigator should include suicidal behavior as part of the verbatim term on the eCRF, that is, "slit wrists/suicidal behavior." Such an event will be collected as an SAE. Acts of self-mutilation or self-injury without suicidal intention, for example, self-imposed cigarette burns, will be collected as nonserious AEs.

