10.1.4 SAEs

An SAE is defined as any untoward medical occurrence that at any dose:

1. Results in DEATH.
2. Is LIFE THREATENING.
 - The term "life threatening" refers to an event in which the subject was at risk of death at the time of the event; it does not refer to an event that hypothetically might have caused death if it were more severe.

3. Requires inpatient HOSPITALIZATION or prolongation of existing hospitalization.
4. Results in persistent or significant DISABILITY/INCAPACITY.
5. Is a CONGENITAL ANOMALY/BIRTH DEFECT.
6. Is an IMPORTANT MEDICAL EVENT that satisfies any of the following:
 - May require intervention to prevent items 1 through 5 above.
 - May expose the subject to danger, even though the event is not immediately life threatening or fatal or does not result in hospitalization.
 - Includes any event or synonym described in the Takeda Medically Significant AE List ([Table 10.a](#)).

Table 10.a Takeda Medically Significant AE List

Term	
Acute respiratory failure/acute respiratory distress syndrome	Hepatic necrosis Acute liver failure
Torsade de pointes/ventricular fibrillation/ventricular tachycardia	Anaphylactic shock Acute renal failure
Malignant hypertension	Pulmonary hypertension
Convulsive seizure	Pulmonary fibrosis
Agranulocytosis	Confirmed or suspected endotoxin shock
Aplastic anemia	Confirmed or suspected transmission of infectious agent by a medicinal product
TEN/SJS	Neuroleptic malignant syndrome/malignant hyperthermia Spontaneous abortion/stillbirth and fetal death

SJS=Stevens-Johnson syndrome, TEN=Toxic epidermal necrolysis.

PTEs that fulfill 1 or more of the serious criteria above are also to be considered SAEs and should be reported and followed up in the same manner (see Sections [10.2.2](#) and [10.3](#)).

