10.2.2 Collection and Reporting of SAEs

When an SAE occurs through the AE collection period it should be reported according to the following procedure:

A Takeda SAE form must be completed, in English, and signed by the investigator immediately or within 24 hours of first onset or notification of the event. The information should be completed as fully as possible but contain, at a minimum:

- A short description of the event and the reason why the event is categorized as serious.
- Subject ID number.
- Investigator's name.
- Name of the study drug(s).
- Causality assessment.

The SAE form should be transmitted within 24 hours to the attention of the contact listed in Section 1.1.

Any SAE spontaneously reported to the investigator following the AE collection period should be reported to the sponsor if considered related to study participation.

Reporting of serious PTEs will follow the procedure described for SAEs.

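### Protocol 10.1.3 classes all self-injury without suicidal intent as nonserious, which contradicts the outcome-based SAE definition in 10.1.4 when the injury is serious

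*Protocol*

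**What the plan says.** Protocol Section 10.1.3 has a bullet on suicidality events. It makes completed suicide an SAE and, for this development program, adds suicide attempts and suicidal intention with a definite plan. It then deals with ideation, and that rule carries an exception: "Unless the event meets other serious criteria, suicidal thoughts or suicidal ideations that do not include a definite plan or action" are nonserious.

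The bullet next asks the investigator to establish intent when a subject presents with self-injury. If the act was suicidal in intent, it is an SAE. If not, the closing sentence applies: "Acts of self-mutilation or self-injury without suicidal intention, for example, self-imposed cigarette burns, will be collected as nonserious AEs". No exception is attached to that sentence.

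Section 10.1.4 follows directly. It opens "An SAE is defined as any untoward medical occurrence that at any dose" and lists outcomes, among them "Is LIFE THREATENING" and "Requires inpatient HOSPITALIZATION or prolongation of existing hospitalization". Section 10.2.2 then sets the reporting duty: "When an SAE occurs through the AE collection period it should be reported according to the following procedure", with a form "signed by the investigator immediately or within 24 hours of first onset or notification of the event". Section 10.2.1.1 includes seriousness among the items documented for every event.

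SAP Section 7.13.1 summarizes treatment-emergent SAEs and lists all SAEs. It gives no seriousness criteria of its own, so it depends on the classification made at the site.

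**The concern.** The self-injury rule has two branches, and intent alone selects between them. Outcome appears in neither. Seriousness in 10.1.4 depends on outcome, whatever the intent. For most minor injuries the two rules agree. For a non-suicidal self-injury that is life threatening, needs inpatient admission or meets another listed criterion, they do not, and an investigator cannot follow both.

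What is at stake is the handling of the individual event. Suicidal ideation and behavior is a stated additional objective (Section 5.1.3), and the C-SSRS is given at every study visit (Section 6.1), so a serious self-injury, with its intent judged by the site, is an event the sponsor would want to see quickly. Two other possible safety nets do not cover it. Self-injury is not one of the special interest AEs in Section 10.1.5 (skin and allergic reactions, liver injury, overdose) that must be reported within 1 business day. Under Section 11.0 there is no data safety monitoring committee.

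**Working it through.** No calculation applies, and the plan states no figure to reproduce. The check is to take one hypothetical event through each rule: a subject injures himself or herself after the first dose, the investigator finds no suicidal intent, and the subject is admitted to hospital.

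| Step | 10.1.3, closing sentence read literally | 10.1.4 with 10.2.2 |
|---|---|---|
| What decides seriousness | Intent | Outcome |
| Classification | Nonserious AE | SAE, by the hospitalization criterion |
| SAE form within 24 hours | Not triggered | Required |
| SAP treatment-emergent SAE table | Not counted | Counted |
| SAP AE listing and TEAE tables | Included | Included |

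Three points settle whether other text removes the conflict.

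1. **Does the ideation exception extend to self-injury?** No. It opens the ideation sentence and belongs grammatically to that sentence. The self-injury sentence is four sentences later in the same bullet and does not repeat it.

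2. **Does the seriousness field in 10.2.1.1 resolve it?** Not by itself. The field records an answer. For this event 10.1.3 supplies one answer and 10.1.4 the other.

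3. **Does 10.2.2 resolve it?** It applies to every SAE and excludes no type of event. But it starts from the event being an SAE, so it inherits the same question.

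Neither 10.1.3 nor 10.1.4 says which prevails. A site may treat the specific sentence as controlling, or the formal definition. The documents support either course, and the result differs in the classification, SAE-form and SAE-table rows above.

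**The case against.** The strongest reply is that the governing definition is intact. Section 10.1.4 covers any event with a listed outcome, 10.2.2 attaches the 24-hour duty to every SAE, and seriousness is recorded for each event. An investigator with an admitted subject has clear grounds to report. The bullet also has a sensible narrower reading. It gives suicidal behavior an automatic upgrade to SAE for this program, and the closing sentence may only mean that self-injury without intent does not receive that upgrade. The cigarette-burn example points to minor injury. The section is headed as additional points to consider, and the formal definition comes next.

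Much of this stands. A reader might infer that a serious non-suicidal self-injury is certain to escape 24-hour reporting and the SAE table. The documents do not support that, because 10.1.4 and 10.2.2 still apply to it. Nor do they support reading the missing exception as deliberate, since an oversight fits equally well. It would also be wrong to say that no expedited route remains: Section 10.3.1 has the sponsor prepare expedited reports for other safety issues that could materially alter the benefit-risk assessment.

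What does not stand is the suggestion that nothing needs correcting. The narrower reading has to be supplied by the reader. The sentence as written covers all such acts, and the same bullet shows how the exception is worded when it is meant to apply.

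**Conclusion.** Wrong as written: an internal contradiction between 10.1.3 and 10.1.4 in how a serious self-injury without suicidal intent is classified. The consequence is a risk of misclassification at sites that follow 10.1.3 literally, and through it a possible missed 24-hour SAE report and an undercount in the treatment-emergent SAE table. The event would not vanish from the data. It would remain in the AE listing and, if treatment-emergent, in the TEAE tables, including those by intensity.

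The size cannot be estimated, because the documents give no expected rate of self-injury or of SAEs. Such events should be rare: treatment lasts 5 weeks, and Section 7.2 excludes subjects with any psychiatric history, significant suicide risk or a past suicide attempt. For illustration only, one event in an arm of 88 is 1/88 = 1.1 percentage points of SAE incidence, assuming all 88 are dosed. The point does not rest on that figure. SAP 7.13.1 plans no test of SAE incidence, and the primary analysis is unaffected. The case for correction rests on the reporting of the individual event.

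**What to change.** Reconcile 10.1.3 with 10.1.4 by making the self-injury sentence subject to the seriousness criteria, in the way the ideation sentence already is. A lead-in clause is enough: *Unless the event meets a seriousness criterion in Section 10.1.4,* placed before the existing sentence. Minor injuries such as the protocol's own example stay nonserious, and suicidal acts stay SAEs.

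The cost is one clause in the protocol and the matching line in any eCRF completion instructions that repeat the rule. No visits, assessments or data fields are added. The SAP needs no change, because it takes seriousness as recorded.

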10.1.4 SAEs

An SAE is defined as any untoward medical occurrence that at any dose:

1. Results in DEATH.
2. Is LIFE THREATENING.
 - The term "life threatening" refers to an event in which the subject was at risk of death at the time of the event; it does not refer to an event that hypothetically might have caused death if it were more severe.

3. Requires inpatient HOSPITALIZATION or prolongation of existing hospitalization.
4. Results in persistent or significant DISABILITY/INCAPACITY.
5. Is a CONGENITAL ANOMALY/BIRTH DEFECT.
6. Is an IMPORTANT MEDICAL EVENT that satisfies any of the following:
 - May require intervention to prevent items 1 through 5 above.
 - May expose the subject to danger, even though the event is not immediately life threatening or fatal or does not result in hospitalization.
 - Includes any event or synonym described in the Takeda Medically Significant AE List ([Table 10.a](#)).

Table 10.a Takeda Medically Significant AE List

Term	
Acute respiratory failure/acute respiratory distress syndrome	Hepatic necrosis Acute liver failure
Torsade de pointes/ventricular fibrillation/ventricular tachycardia	Anaphylactic shock Acute renal failure
Malignant hypertension	Pulmonary hypertension
Convulsive seizure	Pulmonary fibrosis
Agranulocytosis	Confirmed or suspected endotoxin shock
Aplastic anemia	Confirmed or suspected transmission of infectious agent by a medicinal product
TEN/SJS	Neuroleptic malignant syndrome/malignant hyperthermia Spontaneous abortion/stillbirth and fetal death

SJS=Stevens-Johnson syndrome, TEN=Toxic epidermal necrolysis.

PTEs that fulfill 1 or more of the serious criteria above are also to be considered SAEs and should be reported and followed up in the same manner (see Sections [10.2.2](#) and [10.3](#)).

10.1.5 Special Interest Adverse Events

A special interest AE (serious or nonserious) is one of scientific and medical concern specific to the compound or program, for which ongoing monitoring and rapid communication by the investigator to Takeda may be appropriate. Such events may require further investigation in order to characterize and understand them and would be described in protocols and instructions provided for investigators as to how and when they should be reported to Takeda.

10.1.5.1 Skin and Allergic Type Reactions

Any subject who develops rash should undergo assessment to characterize the nature and location of the rash. Subjects should be adequately examined for any clinical features that might suggest a developing drug reaction with eosinophilia and systemic symptoms (DRESS), a developing TEN,

or SJS. For example, all subjects who develop rash should undergo a physical examination and be monitored for the appearance of any of the following features (and findings should be recorded):

- a) Involvement of mucous membranes or conjunctiva.
- b) The development of skin pain.
- c) Urticaria, blistering, other skin lesions.
- d) Any evidence of angioedema.

If there are subjects with symptoms of systemic reaction (eg, generalized rash), or signs of a severe rash (such as those outlined above), or if clinically appropriate, then the following laboratory tests should also be performed and the results monitored accordingly: complete blood count with differentials, liver and renal functions tests, and urinalysis.

Any subjects showing symptoms or signs outlined above, or if clinically indicated, should also be assessed by a dermatologist and undergo an adequate diagnostic work-up (to assess for developing DRESS, TEN, or SJS).

Finally, consider taking photographs of rashes and, when appropriate, obtain skin biopsies.

For all cases of rash where an alternative causality is not known, the Skin- or Allergy-Type Reaction page of the eCRF should be completed within 1 business day of the investigator's awareness of the event. If the alternative causality has been identified, then the Skin- or Allergy-Type Reaction page of the eCRF should not be completed.

10.1.5.2 Liver Injury

Management of liver toxicity AEs is described in Section 7.4. If ALT or AST $>3\times$ ULN, laboratory tests should be repeated within a maximum of 7 days, and preferably within 48 to 72 hours. If the ALT or AST remains elevated $>3\times$ ULN on these 2 consecutive occasions, and this observation cannot be explained by concomitant disease or another alternative causality, the abnormality should be recorded on an AE page of the eCRF. The investigator must contact the medical monitor for consideration of immediate discontinuation of study drug and discussion of relevant subject details and possible alternative causalities.

For events that meet the criteria described in Section 7.4, the Liver Injury page of the eCRF should be completed within 1 business day of the investigator's awareness of the event.

